## Statistical Analysis Plan

Missing values are replaced by multiple imputation including all assessed variables. Outliers are identified by visual inspection and inclusion/exclusion is decided on a case-by-case approach. Estimates are calculated based on 95% confidence intervals.

Feasibility (research question 1) is assessed by frequencies fulfilling the predefined cut-offs (see objectives).

The acceptance score of  $> 2$  is evaluated by Wilcoxon-tests for one sample (one-sided) for all versions of the GTS (-P mean of single sessions and entire therapy, -T, and -TP). Significant changes in primary outcomes psychological flexibility (AAQ-ABI) and psychological burden (DASS-21) are assessed with Wilcoxon-tests for paired samples (one-sided);  $p$ -value is Bonferroni-adjusted ( $p = .025$ ). Significant changes in secondary outcomes valued living (VQ), self-as-context (SACS), depressive symptoms (PHQ-9), and anxiety symptoms (GAD-7) are assessed with Wilcoxon-tests for paired samples (one-sided);  $p$ -value is Bonferroni-adjusted ( $p = .0125$ ). Individual changes in primary and secondary outcomes are also based on reliable change indices with a significance level of  $\alpha = .90$  (one-sided).

Sensitivity analyses examine the influence of the baseline variables age, gender, kind of stroke (ischemia vs. hemorrhage), current use of prescribed psychotropic drugs (yes/no), previous mental disorder (yes/no), and previous use of psychotherapy (yes/no) on changes in primary and secondary outcomes. These bivariate associations are investigated by Pearson correlations (for continuous covariates) and Chi tests (for categorical covariates;  $p = .05$ , two-sided) using the difference scores of the outcomes. Likewise, associations between therapy acceptance and the changes in efficacy outcomes (AAQ-ABI, DASS-21, VQ, SACS, PHQ-9 and GAD-7) are exploratively analyzed.

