## Objectives

The study aims to provide answers to the following research questions

1. Is the group therapy program feasible?
2. Is the group therapy program accepted by stroke survivors and therapists?
3. Are there first indications on the efficacy of the group therapy to improve psychopathology and/or ACT-specific outcome measures?

Feasibility is hereby assessed via quantitative and objective indicators in accordance with a previous study investigating the efficacy of ACT in people with acquired brain damage (Sathananthan et al., 2022). These indicators include recruitment rates ( $\geq 3$  participants per group within six months), drop-out rates  $\leq 20\%$ , group attendance  $\geq 80\%$  (out of 8 participants \* 8 sessions = 64), homework completion rates  $\geq 50\%$  (for each session from participants present in session), completion rates of outcome measures  $\geq 80\%$ , treatment fidelity  $\geq 80\%$  (adherence to objectives and contents listed in the manual). Fidelity ratings are based on video recordings of two randomly selected sessions. A research assistant rates the therapists' behavior according to a checklist developed for that session.

Patients rate therapy acceptance with a validated "group therapy session questionnaire" (GTS-P; Zoubek, 2013), which includes six items for each session assessing for example active involvement and comprehensibility of contents, and two items for the entire group therapy on satisfaction and prospect of success. Therapists rate therapy acceptance with a co-developed questionnaire (GTS-T) including twelve items for each session which assess the same six contents as the patients' questionnaire and additional six items on the therapist's involvement and satisfaction. Therapists also rate acceptance for the entire group therapy for each patient on six items also resembling the six items of the patient session questionnaire (GTS-TP). All items are rated on a five-point Likert scale (0 = not true at all to 4 = absolutely true). Mean ratings in a previous study investigating a group therapy for people with diabetes and depression ranged from 2.26 to 2.86 in the different versions of the questionnaire (Zoubek, 2013). Accordingly, a mean value higher than 2 is considered as adequate therapy acceptance by patients and therapists in this study.

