## Study Design

The study employs a pre-post design without a control group. Consequently, there is no randomization or blinding to conditions. Group therapy is conducted with two groups, each consisting of six individuals. The therapy consists of 8 sessions, each lasting 90 minutes. A 30-minute diagnostic examination with questionnaires, including socio-demographic and health-related data, current psychopathology (depressive symptoms, PHQ-9; Kroenke et al., 2001; psychological burden, DASS-21; Lovibond & Lovibond, 1995; anxiety, GAD-7; Spitzer et al., 2006), and ACT-specific outcomes (valued living, VQ; Smout et al., 2014; psychological flexibility, AAQ-ABI; Sylvester, 2011; self-as-context, SACS; Zettle et al., 2018) takes place just before the first session. AAQ-ABI and SACS were translated into German for the first time according to recommendations using independent forward and backward translations (Wild et al., 2005). The questionnaires PHQ-9, DASS-21, GAD-7, AAQ-ABI, VQ, and SACS were also translated into plain language by a professional translation service ("Office for Easy Language Bethel", Bielefeld). After each session, participants and therapists rate the session using the GTS-P and the GTS-T, respectively. After the last session, all participants answer the same questionnaires as before the first session. They evaluate the entire therapy in the GTS-P and indicate if they would recommend the therapy to a friend with similar complaints (yes/no). The pre- and post-assessments are conducted by a trained assistant to exclude biases from the study therapists as facilitators. After the last session, therapists rate the entire therapy for each patient using the GTS-TP.

In a session form, therapists also record the participation of individual persons (Yes/No) and the completion of homework assignments (Yes/No/Incomplete) for each session. If not completed or incomplete, subjective obstacles are queried and documented. This serves to examine feasibility regarding session adherence and homework completion (objective 1).

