## Selection and Exclusion of Subjects

The participants are recruited through initial consultations at the university's neuropsychological outpatient clinic as well as through self-help groups and practitioners in the region involved in the aftercare of stroke survivors. For this purpose, information flyers are sent to neurological rehabilitation clinics as well as neurological, physiotherapy, occupational therapy, and speech therapy practices. Information and contact details for the study are also published on the homepage of the outpatient clinic and the research unit. Eligibility is evaluated by the principal investigator in an a-priori screening session using relative's information as additional source, if possible.

The study includes N = 12 adult individuals who:

1. have experienced a stroke (ischemic infarction or intracerebral hemorrhage);
2. report increased distress according to the DASS-21;
3. demonstrate sufficient cognitive and linguistic abilities; and
4. show sufficient motivation for therapy.

Increased distress according to the DASS-21 is defined as exceeding a cutoff on at least one of the three subscales of the questionnaire (Depression = D > 10, Anxiety = A > 6, and Stress = S > 10; Nilges & Essau, 2015). In the initial consultation, the cognitive and linguistic performance is assessed based on the participants' self-report and, if applicable, that of a family member, supplemented by the external judgment of the study leader, who has extensive experience in clinical work with individuals with brain damage. If the participant, possibly with input from a family member, and the study leader agree that the person can effectively participate in and benefit from 90-minute group therapy sessions on a weekly basis, the criterion is considered fulfilled. Finally, therapy motivation is assessed by participants assuring their willingness to change their approach to the illness, attend sessions regularly, and complete homework assignments within the therapy program as fully as possible.

Exclusion criteria are assessed based on self-report and external reports by the interested individual, the study leader, and possibly a family member, and include:

1. Interaction or behavioral disorders that significantly hinder group participation (e.g., significantly increased irritability or apathy);
2. Other severe psychiatric disorders (dementia, psychosis, personality disorder, intellectual disability); and

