## Assessment of Efficacy

Study design, sample size, and application of novel questionnaire versions do not allow to sufficiently prove efficacy of the treatment. However, first indicators of efficacy are investigated by pre-/post comparisons of psychological flexibility (AAQ-ABI) and psychological burden (DASS-21). As secondary outcomes, changes in valued living (VQ), self-as-context (SACS), depressive symptoms (PHQ-9), and anxiety symptoms (GAD-7) are examined. Statistically significant changes are considered indicators of efficacy. In addition, number of participants under the cut-offs on DASS-21 (D  $\leq$  10, A  $\leq$  6, S  $\leq$  10), PHQ-9 ( $\leq$  11), and GAD-7 ( $\leq$  11) before and after the therapy are assessed.

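### With 12 patients, undefined case-by-case outlier exclusion leaves the one-sided .025 level uncontrolled, and imputing from every assessed variable leaves an unpenalised model no residual degrees of freedom

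*Combined protocol and SAP*

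**What the plan says.** All the analysis rules are in the Statistical Analysis Plan section.

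- Missing data: "Missing values are replaced by multiple imputation including all assessed variables". No method, predictor list, number of imputations or pooling rule for the Wilcoxon test is given.
- Extreme values: "Outliers are identified by visual inspection and inclusion/exclusion is decided on a case-by-case approach". No threshold, screened score, decision-maker or comparison with and without the excluded value is given.
- Tests: the two primary outcomes (AAQ-ABI, DASS-21) and the four secondary outcomes "are assessed with Wilcoxon-tests for paired samples (one-sided", at .025 and .0125 per test.
- The covariate analyses are run "using the difference scores of the outcomes", so change scores will be in the dataset and could be inspected.

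On sample size, Selection and Exclusion of Subjects states: "The study includes N = 12 adult individuals who" meet its criteria. Study Design describes a single-arm pre-post study without blinding. Assessment of Efficacy concedes that the design cannot sufficiently prove efficacy, but adds: "Statistically significant changes are considered indicators of efficacy".

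**The concern.** One patient is 1/12 = 8% of the sample. The tests are one-sided, so removing one patient who worsened pushes the result towards significance. The signed-rank test already replaces an extreme change by its rank, so exclusion buys little robustness, while an undefined rule costs control of the error rate. At stake is the Bonferroni correction: if each primary test ran at .045, the bound on the chance of at least one false positive would be 2 × .045 = .09, not 2 × .025 = .05.

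The imputation rule raises a different problem. Taken as a list of predictors, it asks for more coefficients than there are patients. The imputed values would then come from whatever reduced or penalised model the software selects, not from the plan.

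**Working it through.** **Plan's own figures.** .05/2 = .025 (two primary tests) and .05/4 = .0125 (four secondary tests). Both reproduce.

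**Exact level without exclusion.** With n = 12 there are 2^12 = 4,096 equally likely sign patterns under no change. W is the sum of the ranks of worsened patients.
- P(W ≤ 13) = 87/4,096 = .0212 and P(W ≤ 14) = 107/4,096 = .0261, so the primary critical value is 13.
- P(W ≤ 10) = 43/4,096 = .0105, so the secondary critical value is 10.
- For 11 and 10 pairs the attained primary levels are .0210 and .0244.

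The stated level therefore holds if every value is kept.

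**Level with exclusion.** The documents give no rule, so everything here is assumed: no true change, normal or t3 scores, and the exact test on the remaining pairs. Every value that the rule flags is dropped, or every flagged worsened patient where so stated. The 1.5-IQR rows (quartiles by linear interpolation) cover pre-post r = .4 to .8; the other rows use r = .6.

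| Rule and scores screened | Primary level (nominal .025) |
|---|---|
| No exclusion | .021 |
| 1.5-IQR, baseline scores | .022-.026 |
| 1.5-IQR, raw pre and post scores, all flagged | .024-.031 |
| 1.5-IQR, raw scores, flagged worsened only | .030-.048 |
| 1.5-IQR, change scores, all flagged | .043-.045 |
| 1.5-IQR, change scores, flagged worsened only | .048-.056 |
| 1.5-IQR with Weibull quartiles, change scores, all flagged | .033-.034 |
| 3-IQR, change scores, all flagged or worsened only | .025-.028 |
| MAD cutoff 2, change scores, all flagged or worsened only | .065-.084 |

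For the secondary tests (exact level .0105), the 1.5-IQR rule gives .012-.014 for baseline screening and .026-.035 for change scores. With 12 pairs it flags at least one change score in 28% of normal datasets and 51-57% of t3 datasets. Change-score screening inflates the level even when both tails are screened: a value far from the bulk tends to lie on the side opposite to the chance shift, and removing it strengthens that shift.

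**Imputation.** With one post-score missing, 11 complete records remain. Residual df = records − (predictors + 1).
- Six pre-scores and the five other post-scores: 11 − 12 = −1.
- Six covariates named in the SAP and six pre-scores: 11 − 13 = −2.
- All of these together: 11 − 18 = −7.
- Same scale's pre-score only: 11 − 2 = 9.

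A literal reading adds more. The baseline assessment is described as "including socio-demographic and health-related data", and the patient questionnaire has "six items for each session assessing for example active involvement", which makes 6 × 8 = 48 ratings per patient.

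**The case against.** Several points count against pressing this hard.

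- **The level range is not a property of the plan.** A reader might infer that the plan's level lies between about .022 and .055, or doubles. The documents do not support that. They state no rule, and a case-by-case decision can keep a flagged value. The figures move with the rule and even with the quartile definition. Nothing suggests that only worsened patients would be dropped. This stands: the figures are illustrations, not limits.
- **The imputation can be run.** A reader might infer that it must fail. It need not: a ridge penalty, predictor selection or matching would give an answer. The sentence could also describe which variables are imputed, not which are predictors, and six pre-scores alone would leave 11 − 7 = 4 df. This also stands. What remains is that the literal predictor reading cannot be fitted without penalty, and that the model actually used is unstated.
- **Missing data are not certain.** The 20% drop-out and 80% completion figures in Objectives are feasibility criteria, neither forecasts nor caps.
- **Efficacy comes third**, after feasibility and acceptance, and significance is read only as a first indication. This limits the consequence but does not remove it, because significance is still the plan's stated indicator.
- **Imputation need not be the primary analysis.** With two milder patients missing (assumed correlation .5 of drop-out with the pre-score, normal scores), pre-score imputation has level .025-.027 and observed pairs .032-.039. With skewed scores (assumed lognormal) and two more-distressed patients missing, imputation has about .026-.030 and observed pairs .014-.018. Either order is defensible.

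**Conclusion.** The concern holds in a limited form. Visual, case-by-case exclusion before one-sided rank tests leaves the .025 level uncontrolled at N = 12, for little gain in robustness. Under the assumed 1.5-IQR rule the effect runs from negligible (baseline screening) to roughly twice the nominal level (dropping only flagged worsened patients on change scores). A 3-IQR rule on change scores does almost no harm, and MAD rules reach about .08. Which of these applies cannot be determined from the documents.

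The imputation point rests on plain counting, but it binds only for an unpenalised model, only if every assessed variable is meant as a predictor, and only if data are missing. Both rules should be tightened before the data are viewed. Neither undermines the feasibility or acceptance aims.

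**What to change.** 1. Keep every genuine value in the primary and secondary signed-rank tests. Correct or remove only verified data errors. Report any run without an extreme value as a labelled sensitivity analysis.
2. Replace the open predictor list by a small pre-specified model. One example is a normal model with the same scale's pre-score as the only predictor, 20 imputations, and the Wilcoxon z pooled by Rubin's rules: mean z / sqrt(1 + (1 + 1/20)B), compared with 1.96, where B is the between-imputation variance of z. Report it beside the exact observed-pairs test and name in advance which is primary. If nothing is missing, only the exact test is needed.
3. If post-scores are missing, report how much worsening in those patients would remove significance. For example, if the other 11 all improved, one missing patient at the worst rank gives W = 12, p = 70/4,096 = .017, still significant. If the other 10 all improved, two missing patients at ranks 6 and 7 give W = 13, p = .021; at ranks 7 and 8 they give W = 15, p = .032.

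The cost is a few sentences of SAP text and no new data. Imputation gains almost no power: for an assumed change of 0.8 SD (r = .6) with two missing it is .70 against .69 for observed pairs, compared with .76 for all 12 pairs. Neither analysis protects against drop-out related to worsening. With two missing and an assumed correlation of .5, the false-positive rate is .051-.056 for imputation and .059-.063 for observed pairs, which is why step 3 is needed.

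### Bonferroni within each outcome family is valid, but Holm at the same family-wise level of .05 would detect more when several outcomes change together: an optional, cheap improvement

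*Combined protocol and SAP*

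**What the plan says.** The Statistical Analysis Plan section defines two families. The first is the "primary outcomes psychological flexibility (AAQ-ABI) and psychological burden (DASS-21"), for which the threshold is given as "value is Bonferroni-adjusted ( $p = .025"). The second is the "secondary outcomes valued living (VQ), self-as-context (SACS), depressive symptoms (PHQ-9), and anxiety symptoms (GAD-7"), with the threshold given as "value is Bonferroni-adjusted ( $p = .0125"). Both use "Wilcoxon-tests for paired samples (one-sided"). No step-down procedure is mentioned and no reason is given for the single-step one.

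The Assessment of Efficacy section states how the results are read: "Statistically significant changes are considered indicators of efficacy". Significance is thus read outcome by outcome, with no rule requiring several outcomes to succeed jointly. The same section says that the design, the sample size and the new questionnaire versions cannot sufficiently prove efficacy. On size and design: "The study includes N = 12 adult individuals who" meet the entry criteria, and "The study employs a pre-post design without a control group".

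**The concern.** Single-step Bonferroni holds every outcome in a family to the same strict threshold, whatever the other outcomes show. Holm starts at that threshold and relaxes it after each rejection, for the same family-wise guarantee and without any assumption about how the outcomes correlate. If one primary has p at or below .025 and the other lies between .025 and .05, Bonferroni reports one indicator of efficacy and Holm reports two.

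This bears on research question 3, which asks about psychopathology and ACT-specific measures. Each primary covers one of these domains (DASS-21 and AAQ-ABI), so whether one or both reach significance changes the answer. At stake is the detection of a second or later changed outcome in a small pilot.

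**Working it through.** **1. The plan's thresholds.** With a family-wise level of .05 (implied by the thresholds, not stated): .05/2 = .025 for two primaries and .05/4 = .0125 for four secondaries. Both reproduce exactly. If tests are independent and use the full threshold, the family-wise error is 1 − (1 − .025)² = 4.94% and 1 − (1 − .0125)⁴ = 4.91%. Bonferroni does its job.

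**2. Holm's thresholds.** Order the m p-values and compare the k-th smallest with .05/(m − k + 1), stopping at the first failure.
- Primary family: .05/2 = .025, then .05/1 = .05.
- Secondary family: .05/4 = .0125, .05/3 = .0167, .05/2 = .025, .05/1 = .05.

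The first threshold is Bonferroni's and the later ones are larger. Two things follow without simulation. Holm rejects everything Bonferroni rejects. If Bonferroni rejects nothing in a family, neither does Holm.

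**3. Size of the gain.** From the plan: N = 12, one-sided paired Wilcoxon tests, families of 2 and 4. Multiple imputation is planned, so N is kept at 12. Assumed, because the documents give no values: normal change scores, the same standardised change on every outcome, and correlation .5 (range 0 to .8 in brackets). Power was simulated with 100,000 trials per scenario and the exact signed-rank null distribution.

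| Standardised change | Per primary, Bonferroni → Holm | Per secondary, Bonferroni → Holm |
|---|---|---|
| 0.3 | 14% → 16% (13–14% → 15–16%) | 8% → 10% (8% → 9–10%) |
| 0.5 | 31% → 37% (31% → 36–37%) | 21% → 26% (21% → 24–27%) |
| 0.8 | 67% → 75% (67% → 73–76%) | 53% → 65% (54% → 64–67%) |
| 1.0 | 85% → 91% (85% → 89–92%) | 75% → 86% (75% → 84–89%) |

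The 53% and 54% at 0.8 differ only by simulation error and rounding.

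**4. At least one significant outcome.** This is the same under both methods in every scenario. At change 0.8 and correlation .5 it is 83% for the primaries and 85% for the secondaries. The whole gain therefore lies in later rejections. With two outcomes, mean power per outcome is (chance of at least one + chance of both)/2. At change 0.8 the chance of both goes from 51% to 66%: (83 + 51)/2 = 67% and (83 + 66)/2 = 74.5%, which agrees with the table.

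**5. Only one primary changes.** With a change of 0.8 on one primary and none on the other, power for the changed one rises by at most 0.3 points. At correlation .5, the false-positive rate of the unchanged one rises from 2.1% to 4.3%. The exact distribution explains the limits. There are 2¹² = 4,096 sign patterns, without ties or zero changes. Of these, 87 have a one-sided p at or below .025 (87/4,096 = .0212) and 189 at or below .05 (189/4,096 = .0461). Holm can never reject an outcome with p above .05, so the unchanged outcome's rate cannot exceed .0461 apart from simulation error.

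**6. Nothing changes at all.** The family-wise error is identical under the two methods: about .04 in each family at correlation .5.

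**7. Smaller N.** At n = 10 and change 0.8, power goes from 60% to 65–66% per primary and from 41% to 52–54% per secondary. The pattern is the same, so it is not peculiar to N = 12.

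**The case against.** The strongest reply is that nothing here is wrong. The families are defined, the thresholds are right, and choosing between two valid prespecified procedures is largely preference in a pilot that disclaims proof of efficacy. That stands, and it sets the weight of the point.

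A reader might infer that Bonferroni tilts the study towards a false verdict of no indication of efficacy. The plan does not support that: Holm's first step is the Bonferroni step, so a family with no finding under one has none under the other. A reader might also take the larger jumps in the chance that all outcomes succeed (51% to 66% for both primaries) as the relevant loss. The plan has no such success rule, so the per-outcome figures are the ones to use.

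Two costs of Holm also stand. First, the false-positive rate of an unchanged outcome rises when its neighbour changes. That case is plausible here. Participants enter by exceeding a DASS-21 cutoff, DASS-21 is a primary outcome, and there is no control group, so regression to the mean alone could make DASS-21 significant and relax the AAQ-ABI threshold to .05. Second, the SAP plans 95% confidence intervals. If these are conventional two-sided intervals (an assumption), they match a one-sided .025 test. Under Holm, a primary with p between .025 and .05 could be called significant although its interval includes no change. Neither cost breaks the family-wise level of .05.

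**Conclusion.** The plan's adjustment is valid. Holm is a modest improvement on it: the same family-wise guarantee under any correlation, never fewer rejections, and more power for second and later outcomes when several change together. The gain per primary outcome is about 2 points at a standardised change of 0.3, 6 at 0.5 and 8 at 0.8. Per secondary outcome it is about 5 points at 0.5 and 12 at 0.8. It is about zero if only one primary changes, and exactly zero for finding at least one significant outcome.

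That Holm dominates and that the chance of any finding is unchanged are mathematical facts. The sizes rest on assumed effect sizes, correlations, equal change on all outcomes and normal change scores. It would go too far to say that Holm gives clearly more power at N = 12 without conditions, or that it is free of any downside. Severity: optional.

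**What to change.** In the Statistical Analysis Plan section, replace the two Bonferroni statements with:

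*Within the primary family (2 tests) and within the secondary family (4 tests), one-sided p-values are tested by the Holm procedure at a family-wise level of .05.*

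Add:

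*The 95% confidence intervals are not adjusted for multiplicity and may not match the Holm decisions.*

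The cost is two sentences, with no new data, participants or assumptions. The price in error terms is the higher false-positive rate of an unchanged outcome beside a changed one, within .05. The change should be made before outcome data are analysed, because a later switch could look driven by the results. If the sponsor prefers the stricter per-outcome rate and the match with the intervals, keeping Bonferroni is defensible, and one sentence giving that reason would be enough.

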The manual was translated into German and adjusted to the needs of stroke survivors, who often have a higher age, more comorbidities, and specific neurological impairments compared to the general group of brain-damaged individuals. To reduce cognitive load and adapt to conventions in the German healthcare system, the session duration is shortened from 165 minutes to 90 minutes. Additionally, the study tests outcome questionnaires translated into German and/or simple language for the first time to adjust them to the participants' cognitive capacity.

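### Reliable change indices are planned on first-use questionnaire versions with no reliability specified, so their false-improvement rate is not assured and could err in either direction

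*Combined protocol and SAP*

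**What the plan says.** The Statistical Analysis Plan adds an individual-level analysis to the group-level Wilcoxon tests: "Individual changes in primary and secondary outcomes are also based on reliable change indices". It covers the two primary outcomes (AAQ-ABI, DASS-21) and the four secondary ones (VQ, SACS, PHQ-9, GAD-7). The level is given as α = .90, one-sided. The plan gives no formula, reliability value, type of reliability, SD or source.

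On the instruments, Study Design says that "AAQ-ABI and SACS were translated into German for the first time according to recommendations using independent forward and backward translations". It continues: "The questionnaires PHQ-9, DASS-21, GAD-7, AAQ-ABI, VQ, and SACS were also translated into plain language by a professional translation service". The Background presents this as part of the study's purpose: "the study tests outcome questionnaires translated into German and/or simple language for the first time".

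Two design facts limit what the study can learn about reliability. The sample is small ("The study includes N = 12 adult individuals who" meet the listed criteria), and "The study employs a pre-post design without a control group", so nobody is retested without treatment. The only planned indicator that bears on the questionnaires themselves is the feasibility criterion in Objectives that at least 80% of outcome measures are completed.

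**The concern.** A reliable change index asks whether a person's change exceeds what measurement error alone would produce. Its cut-off follows directly from the reliability put into it. Here the versions administered are new and the plan does not say which reliability will be used.

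There are two usual ways to fill the gap. One is a coefficient from another version of the scale, which need not apply to a new translation or a plain-language rewording. The other is an estimate from these 12 people, which is imprecise. Neither supports a single count of reliably improved participants at a known error rate. Because the choice is open, it could also be made after the results are seen.

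At stake is how the individual-change result is read, including on the primary AAQ-ABI. In a pilot of 12, three people reported as reliably improved could look encouraging, and that count may depend heavily on the coefficient chosen.

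**Working it through.** **Inputs from the documents.** N = 12; level α = .90, one-sided; no control group. No reliability or SD is given, so the plan's cut-off cannot be reproduced. The reliabilities below are assumptions.

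**Reading the level.** Taken literally, a one-sided significance level of .90 gives a critical value of −1.28, and 90% of unchanged people would count as improved. That cannot be meant. I read it as 90% one-sided confidence: critical value 1.2816, nominal false-improvement rate 10%, or 12 × 0.10 = 1.2 people per scale if nobody truly changes.

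**Formula (standard form, assumed because the plan gives none).** Index = (post − pre) / [SD × √(2(1 − r))]. The change needed to be called reliable is 1.2816 × √(2(1 − r)) in SD units:

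- r = .90: 1.2816 × √0.20 = 0.57 SD
- r = .80: 1.2816 × √0.40 = 0.81 SD
- r = .70: 1.2816 × √0.60 = 0.99 SD

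**Actual rate when the reliability used differs from the true one.** With normal errors, a correct SD and no true change, rate = 1 − Φ(1.2816 × √[(1 − r used)/(1 − r true)]).

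Worked case, .90 used and .75 true: √(0.10/0.25) = 0.632; 1.2816 × 0.632 = 0.81; 1 − Φ(0.81) = 20.9%; 12 × 0.209 = 2.5 people.

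| r used | r true | False-improvement rate | Expected of 12 |
|---|---|---|---|
| .90 | .90 | 10.0% | 1.2 |
| .90 | .80 | 18.2% | 2.2 |
| .90 | .75 | 20.9% | 2.5 |
| .90 | .70 | 23.0% | 2.8 |
| .80 | .70 | 14.8% | 1.8 |
| .80 | .90 | 3.5% | 0.4 |
| .70 | .90 | 1.3% | 0.2 |

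The error runs both ways: too many false improvers if the new version is less reliable than assumed, too few if it is more reliable.

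**Three or more false improvers.** If all 12 are unchanged and independent, the chance of at least three on one scale is 11% at a rate of 10.0%, and 47% at a rate of 20.9%.

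**Can the study supply its own reliability?** The pre-assessment allows an internal consistency estimate. With n = 12 and 9 items assumed, the Feldt 95% interval is .57 to .93 around an observed .80, .68 to .95 around .85, and .79 to .97 around .90. Assuming 7 to 21 items instead changes this little (.85: lower limit .67 to .69, upper limit about .95). The pre-post correlation cannot serve as a clean retest coefficient, because everyone is treated in between. A single in-sample estimate therefore does not secure the 10% rate.

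**The case against.** The strongest reply is that this is a missing detail in a supplementary description. Assessment of Efficacy takes statistically significant group changes as the indicator of efficacy, and the Wilcoxon tests use no reliability coefficient. The same section names the novel questionnaire versions among the reasons why efficacy cannot be proven. No decision rule depends on the indices. In the less favourable cases above, the difference is about 1.3 to 1.6 people per scale (2.5 − 1.2 and 2.8 − 1.2). All of this stands, and it limits the weight of the point. It does not remove it: the general caveat does not mention reliability, and the indices are still planned for all six scales.

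A reader might infer more than the documents support in four ways.

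- That the false-improvement rate is wrong or inflated. The documents give no reliability, so the rate may be above, at or below 10%, and the 10% is itself a reading of the stated level.
- That the analysis must borrow coefficients from other versions. The plan does not say so; an in-sample estimate is open to the authors, though imprecise.
- That the reliability of the new versions is known to be unestablished. This would be an inference from silence.
- That the Background promises a reliability study. It says the versions are tested, with the participants' cognitive capacity in view. None of the three research questions concerns psychometrics, and the completion criterion bears on usability.

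**Conclusion.** The point holds in a limited form. The plan applies an analysis that depends on reliability to first-use versions of its scales without fixing or estimating any reliability. The intended error rate is therefore not assured. If the intended rate is 10%, the actual rate could plausibly lie between about 3.5% (.80 used, .90 true) and about 21% to 23% (.90 used, .75 or .70 true). These figures rest on assumed reliabilities, the standard formula, normal errors, a correct SD and no true change.

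A stricter remedy is tempting but not warranted. Calling change reliable only at the lowest reliability considered would cut false improvement to 1.3% if .70 is used and .90 is true, far below 10%. Withholding any claim where the count depends on the reliability would usually delete the result. With normal changes, a common mean improvement of 0 to 0.8 SD and true reliability of .70 to .90, at least one of 12 people falls between the 0.57 and 0.99 SD cut-offs in about 66% to 99% of studies. Showing the range is the proportionate answer.

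**What to change.** In the Statistical Analysis Plan:

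1. Correct the level. If 90% one-sided confidence is meant, write one-sided α = .10 (critical value 1.28).
2. Before the data are seen, fix for each scale the formula, the SD and its source, and the primary reliability with its type (internal consistency or test-retest) and source.
3. Report the internal consistency of each version from the pre-assessment, with its 95% interval.
4. Beside the primary count, report the number reliably changed at reliability .70, .80 and .90.
5. Describe individual change as that range, not as a single count.

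This takes a few lines of analysis on data the study already plans to collect. The price is a less definite individual-change result. The Wilcoxon tests need no change.
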